3. Visual acuity, measured in each eye without cycloplegia within 7 days prior to enrollment using the ATS single-surround HOTV letter protocol as follows:
 - Visual acuity in the amblyopic eye between 20/100 and 20/400 inclusive
 - Visual acuity in the sound eye 20/32 or better
4. Spectacle correction (if applicable) for measurement of enrollment visual acuity must meet the following criteria and be based on a cycloplegic refraction within 6 months:
 - Requirements for spectacle correction:
 - For patients meeting criteria for only strabismus (see 2.2 #2 above)
 - i. Hypermetropia if corrected must not be undercorrected by more than +1.50 D spherical equivalent, and the reduction in plus sphere must be symmetric in the two eyes. Otherwise, spectacle correction is at investigator discretion.
 - For patients meeting criteria for anisometropia or combined-mechanism (see 2.2 #2 above)
 - i. Spherical equivalent must be within 0.50 D of fully correcting the anisometropia
 - ii. Hypermetropia must not be undercorrected by more than +1.50 D spherical equivalent, and reduction in plus must be symmetric in the two eyes
 - iii. Cylinder power in both eyes must be within 0.50 D of fully correcting the astigmatism
 - iv. Cylinder axis in the spectacle lenses in both eyes must be within 6 degrees of the axis of the cycloplegic refraction
 - 5. Wearing optimal spectacle correction for a minimum of 4 weeks at the time of enrollment.
 - 6. Gestational age > 34 weeks and birth weight > 1500 grams
 - 7. Parent willing to accept randomization
 - 8. Parent willing to be contacted and has access to phone
 - 9. Parent does not anticipate relocation outside area of active study site

If patients are in the deprivation amblyopia category, the following criteria must be met for the patient to be enrolled in the study:

Efficacy of Intermittent Occlusion Therapy Glasses for Amblyopia-Dense, Deprivation and Myopic Anisometropia

Amblyopia

Approved 02/08/16

Amended: 05/12/16; 06/27/16; 06/29/16; 07/26/16, 09/13/16, 09/19/16, 09/27/16, 12/15/16, 01/26/17, 03/02/17, 06/20/17, 11/1/17, 12/19/17, 08/27/18, 12/18/18

- a) Age 3 to < 8 years
- b) Amblyopia due to previous congenital or developmental cataract surgery.
- c) Visual acuity, measured in each eye without cycloplegia within 7 days prior to enrollment using the ATS single-surround HOTV letter protocol as follows:
 - a. Visual acuity in the amblyopic eye between 20/40 and 20/400 inclusive

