After randomization, all patients (from both severe amblyopia and deprivation amblyopia groups) will have the following study visits/interactions:

Telephone Call

- Each patient will be contacted by the coordinator via telephone 4 weeks following the beginning of treatment to answer any questions and to encourage compliance with treatment.
- 12 ± 1 weeks after treatment begins : primary outcome visit

Primary Outcome Visit (occurs 12 ± 1 weeks after treatment begins)

Testing will include the following:

1. Visual acuity

Measured in each eye (worse eye first) by a certified examiner using the ATS single-surround HOTV acuity protocol.

2. Titmus fly and Randot Preschool Stereoacuity test

3. Ocular alignment assessed with the SPCT

4. Re-testing of visual acuity in the amblyopic eye (if indicated)

If amblyopic eye visual acuity has not improved from randomization by at least one line, then the acuity will be re-tested at this visit.

The results of the re-test will be used only to determine if the patient will continue study participation with the same study-mandated treatment. The first visual acuity will be used as the primary outcome visual acuity. If neither the test nor the re-test is one line better than the visual acuity at treatment, then study participation ends.

Efficacy of Intermittent Occlusion Therapy Glasses for Amblyopia-Dense, Deprivation and Myopic Anisometropia

Amblyopia

Approved 02/08/16

Amended: 05/12/16; 06/27/16; 06/29/16; 07/26/16, 09/13/16, 09/19/16, 09/27/16, 12/15/16, 01/26/17, 03/02/17, 06/20/17, 11/1/17, 12/19/17, 08/27/18, 12/18/18

Follow-Up Visits after the Primary Outcome Visit

For patients in either treatment group with at least one line of improvement in amblyopic eye acuity at the primary outcome examination, follow-up visits will occur every 12 ± 1 weeks until no improvement of one or more lines is seen.

At each post-primary outcome visit, visual acuity will be measured in each eye (worse eye first) by a certified examiner using the ATS single-surround HOTV acuity protocol. Acuity in the amblyopic eye will be re-tested during the visit if visual acuity has not improved from the last visit by at least one line.

Future treatment plans depend on each visual outcome in the amblyopic eye:

- If the patient's vision in the amblyopic eye is improved 1-2 lines, continue the study for another 12 weeks;
- If no improvement for one visit, continue the study for another 12 weeks;
- If no improvement for two visits, stop.

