Ocular alignment will be assessed at baseline and at 12 weeks after randomization. Development of new strabismus (no tropia at baseline and the presence of near and/or distance tropia at follow-up) or an increase from baseline ≥ 10 PD will be tabulated by treatment group. Similarly, disappearance of a heterotropia and a decrease in the angle of a preexisting strabismus by ≥ 10 PD will be tabulated.

Sample Size:

The sample size for this study was calculated based on a standard two-sided trial with a continuous outcome. The calculations assume 5% type I error with 80% power; the standard deviation of change from the baseline was 0.14, and the effective size difference was 0.12. Therefore, we anticipate that we will require 46 total subjects (i.e., 23 for each group).⁴ Because the IO therapy glasses are a novel device used to treat severe amblyopia, we are uncertain how many 3-8 year-old patients will drop out from the study. According to an average 15% dropout rate in previous amblyopia studies^{1, 6}, we overestimate the sample size to be 28 in each group to account for attrition.

12. **Drugs and Devices.** Does this study involve investigational drugs or devices (test articles) and/or FDA approved drugs/devices used for off-label purposes? If the study involves a test article, identify the drug/device, provide the IND or IDE number and identify the holder of the number. If the study involves drugs/devices used for off-label purposes, this should be stated. If the study does not involve any test articles or drugs/devices used for off-label purposes, this should be stated. *Note: Research involving investigational drugs must comply with the FDA IND Regulations (21 CFR 312) govern research with medical devices. The FDA IDE Regulations (21 CFR 812) govern research with medical devices. In some cases it may be in the best interest of the subject and the investigator for an IND/IDE to be submitted to FDA even when there is no legal requirement.*

Yes. We use IO-therapy glasses and thermosensor. We attach the medical device form of IO-therapy glasses and thermosensor. IO-therapy glasses are FDA approved.

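### The primary acuity analysis is known only from a sample-size calculation on raw change; no model or baseline adjustment is stated, which may cost precision

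*Combined protocol and SAP*

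**What the plan says.** The Sample Size paragraph of Section 11 is the only place in the available text that describes how the two randomised arms are to be compared on acuity. The size was "calculated based on a standard two-sided trial with a continuous outcome". "The calculations assume 5% type I error with 80% power", and "the standard deviation of change from the baseline was 0.14, and the effective size difference was 0.12". This leads to 23 children per group, raised to 28 for 15% dropout. No unit is attached to 0.14 and 0.12; I read them as logMAR.

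Other relevant places:

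- **Outcome.** The Primary Outcome Visit text settles which reading counts: "The first visual acuity will be used as the primary outcome visual acuity". It does not say whether the 12-week level or the change from baseline is analysed.
- **Tests named.** The one between-group test named is the exact Wilcoxon test, and it is for stereoacuity. Sound-eye loss and alignment changes are tabulated.
- **Range of baseline.** Section 8, item 3 for severe amblyopia: "Visual acuity in the amblyopic eye between 20/100 and 20/400 inclusive".
- **Allocation.** Section 3 and the Randomization text describe a computer-generated block design. Stratification by acuity is not mentioned.
- **Availability of baseline.** Delay in Randomization requires acuity within 7 days before randomisation, as a baseline measure, so the covariate will exist for every randomised child.

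**The concern.** A comparison of raw change adjusts for baseline with the slope fixed at 1. If children who start worse tend to gain more, change is still correlated with baseline. A difference in baseline means between arms then leaves a trace in the estimated effect, and variance that a covariate could explain stays in the error term. With 23 to 28 children per arm and a six-line entry range, neither effect can be dismissed in advance.

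Because the model is not named, at least three analyses fit the text: 12-week level, change, and 12-week level adjusted for baseline. They differ in precision, and in a trial this small the choice should be made before the data are seen.

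**Working it through.** **1. Reproduce the plan's figure.** Inputs from Sample Size: difference 0.12, SD 0.14, two-sided 5%, power 80%. The two-sample t-test calculation gives 22.37, so 23 per group, with power 81.1% at 23. For dropout, 23 / 0.85 = 27.06, so 28 per group. Both figures match. If all 28 per group were analysed, unadjusted power would be 88.3%.

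**2. Width of the baseline range.** log10(100/20) = 0.70 and log10(400/20) = 1.30, a span of 0.60 logMAR or six 0.1-logMAR lines.

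**3. Assumptions, none of them in the documents.** Baseline SD (SDb) 0.15 to 0.20 logMAR; a uniform spread over the range would give 0.60/√12 = 0.173. Slope b of change on baseline 0 to -0.4. SD of change held at 0.14. 23 analysed per arm.

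**4. Precision.** Residual SD after adjustment = √(0.14² − b²·SDb²). Putting this straight into the t-test formula is slightly optimistic, because estimating the slope adds about 1/(46 − 4) = 2.4% to the variance. The power figures below are therefore simulated, with normal data; unadjusted power is about 81% in every row.

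| SDb | b | Residual SD | Adjusted power |
|---|---|---|---|
| any | 0 | 0.140 | about 80% |
| 0.15 | -0.1 | 0.139 | about 81% |
| 0.20 | -0.1 | 0.139 | about 81% |
| 0.173 | -0.3 | 0.130 | about 86% |
| 0.20 | -0.4 | 0.115 | about 93% |

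At slope 0, adjustment loses about one point. At -0.1 there is no gain. From there the gain grows with the slope.

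**5. Cross-check by another route.** With equal SDs at baseline and 12 weeks and correlation ρ between them, residual SD = 0.14·√((1+ρ)/2). This gives 0.121 at ρ = 0.5 and 0.133 at ρ = 0.8, with power at 23 per arm of 90.7% and 85.0% (ignoring slope estimation). The order of magnitude agrees.

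**6. Chance imbalance, middle case (SDb 0.173, b = -0.3).**

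- SE of the difference in baseline means: 0.173·√(2/23) = 0.051.
- An imbalance of 2 SE, roughly a 1-in-20 event, is 0.10 logMAR.
- Shift in the raw-change estimate: 0.3 × 0.102 = 0.031, and 0.031/0.12 is about a quarter of the target difference.
- An imbalance of 1 SE shifts it by 0.015.
- For scale, the SE of the raw-change difference itself is 0.14·√(2/23) = 0.041.

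**7. If the 12-week level were compared without adjustment.** Taking its SD as 0.15 to 0.20 (again an assumption), power at 23 per arm would be about 76% to 51%.

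**The case against.** The strongest reply is that the plan has made no poor choice here, because it has stated no choice. Sizing on the SD of change does not bind the analyst to an unadjusted test. If a baseline-adjusted model were used on the same numbers, 28 per arm would usually be conservative. That stands: a reader might infer that the trial has decided to give up precision, but the documents do not say so.

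A reader might also infer that the sample size is wrong or that a change-score comparison is biased. Neither follows. The size reproduces exactly, and under randomisation an unadjusted comparison of change is unbiased with correct type I error.

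Nor does a baseline imbalance pass whole into the estimate. A change score already removes most of it, and only the slope times the imbalance remains, 30% in the middle case. Even the 2-SE shift is smaller than one standard error of the raw difference. That variation is already part of the standard error of a change score, so lost precision and exposure to imbalance are two views of one cost and must not be added.

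Finally, the gain rests on a baseline SD and slope found nowhere in the documents, and Section 3 calls the severe-amblyopia study a pilot. This is fair, and is why the range includes slope 0, where adjustment does slight harm.

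What remains is that the model is unstated, the covariate is already collected, and the possible loss from adjusting is much smaller than the possible gain.

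**Conclusion.** The concern holds as a gap in specification with a likely but unproven cost in efficiency. It is not an error in the sample size or a threat to validity. Under the assumptions in step 3, adjustment changes power at 23 per arm from 81% to somewhere between about 80% and about 93%, with about 86% at SDb 0.173 and slope -0.3. In that middle case an uncommon imbalance of 0.10 logMAR moves an unadjusted change estimate by 0.03 against a target of 0.12.

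The slope drives all of this and the documents give no value for it. Section 3 also says the sample size was taken over from the moderate-amblyopia calculation, so whether an SD of 0.14 applies to severe amblyopia is not shown. That is a further reason to protect precision, though it does not show the trial to be underpowered.

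**What to change.** Add a primary-analysis statement to Section 11: a linear model of 12-week amblyopic-eye logMAR acuity (the first test at that visit) on randomised arm, with baseline amblyopic-eye logMAR acuity as a covariate, reporting the adjusted difference with its 95% CI. Keep raw change by arm as a descriptive summary.

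The cost is one or two sentences, with no new data, no extra children and no change to any study procedure. The statistical downside is about one percentage point of power if change proves unrelated to baseline. The sample size can stay as it is.

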Children ages 3 to < 8 years with **myopic anisometropic amblyopia** will be enrolled into an intermittent occlusion therapy glasses (Amblyz™) group.

2. Background.

Amblyopia is the most common cause of monocular visual impairment in children. The major cause of amblyopia is due to the fact that unbalanced visual experience at an early age induces the mal-development of the neural system. The primary goal of amblyopia treatment is to restore normal visual function both in the visual acuity of the amblyopic (weak) eye and in the binocular cooperation between the eyes.

Current and accepted treatments attempt to enforce the utilization of the amblyopic (weak) eye by obstructing or blurring the vision of the sound eye using eye patching or penalization drops. In these ways, visual experience of the amblyopic eye is enhanced. The mal-development of the neural system can be reversed, at least to some extent, during the plastic period (from birth to 10 years of age) of the visual cortex.

Although these existing treatments are effective, many children fail to achieve normal visual acuity in the amblyopic eye. ^{1,2} Thus, effective treatment for amblyopia, particularly severe amblyopia is in an urgent need.

Electronic eyeglasses, IO-therapy glasses (Amblyz™), are a new medical device designed to treat amblyopia. They are based on intermittent shutting of one of the lenses, which are made of high-tech liquid crystal material. IO-therapy glasses are formed in shape of glasses to facilitate its use and worn the same way as normal optical glasses. The technology was tested in clinical settings and was proven to be safe and efficient.^{3,4}

Benefits of IO-therapy Glasses

1. Periodical occlusion is more convenient to the child in his daily activities thus increases compliance.

Efficacy of Intermittent Occlusion Therapy Glasses for Amblyopia-Dense, Deprivation and Myopic Anisometropia

Amblyopia

Approved 02/08/16

Amended: 05/12/16; 06/27/16; 06/29/16; 07/26/16, 09/13/16, 09/19/16, 09/27/16, 12/15/16, 01/26/17, 03/02/17, 06/20/17, 11/1/17, 12/19/17, 08/27/18, 12/18/18

2. Periodical occlusion enforces binocular vision exercise.
3. Technology allows patient/child to enjoy an active, normal lifestyle.
4. No allergy issues as with an eye-patch.

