- Treatment is continued until there is no further improvement in amblyopic eye acuity (improvement defined as >1 line) between two consecutive 12-week visits, confirmed by a re-test. Once there is no improvement of one or more lines, the patient's participation in the study is over and treatment is at investigator's discretion.

Notes

1. The study will provide patches or IO-therapy glasses.
2. If a patient is noncompliant with treatment, the parents should be encouraged to persist with their efforts to treat to the best of their ability.
3. Prior to deviating from the treatment protocols or prescribing non-protocol treatment, the situation should be discussed with the PI.

Efficacy of Intermittent Occlusion Therapy Glasses for Amblyopia-Dense, Deprivation and Myopic Anisometropia

Amblyopia

Approved 02/08/16

Amended: 05/12/16; 06/27/16; 06/29/16; 07/26/16, 09/13/16, 09/19/16, 09/27/16, 12/15/16, 01/26/17, 03/02/17, 06/20/17, 11/1/17, 12/19/17, 08/27/18, 12/18/18

Randomization of Eligible Patients

1. Once a patient is randomized, the patient will be included in the analysis regardless of whether the assigned treatment is received or not. That is to adhere to “intent-to-treat” design. Thus, the investigator must not randomize a patient until he/she is convinced that the parent/guardian will accept and comply with either of the treatment regimens. Regardless of whether the patient receives the assigned treatment or not, the patient is still considered enrolled in the study and every effort should be made to perform the follow-up examinations according to the study protocol.
2. A patient is officially enrolled when the randomization process is completed.

Delay in Randomization

1. Visual acuity testing and the ocular motility examination must be performed no more than 7 days prior to randomization. If randomization is delayed beyond 7 days, then these tests must be repeated to confirm eligibility and establish the baseline measures for the study.
2. No other parts of the examination (including the refraction) need to be repeated if they were performed within 6 months prior to randomization.

Compliance

A calendar log will be maintained by all families. These logs will be reviewed at each of the protocol visits. The investigator's assessment of compliance will be recorded on the Follow-up Examination Form.

Follow-up Interactions

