Study participation will end only after a post-primary outcome visit at which amblyopic eye acuity shows no improvement of one or more lines on both an initial test and on a confirmatory re-test.

For all follow-up visits:

- Compliance will be evaluated with calendar log and microsensor.
- For patients who wear glasses with microsensors attached, data will be logged by connecting the microsensors to the reading station via antenna at 2-3 cm distance from the antenna. A USB cable transfers the data to a PC for storage; wearing times will be evaluated using the TheraMon® Software and compared to the wearing times protocol. Data will be recorded on the Follow-up Examination Form.

Test	Visit / Interaction			
	Enrollment	4 wk phone call	Primary Outcome 12 ± 1 wk (by masked examiner)	Every 12 ± 1 wks after primary outcome** (by masked examiner)
Telephone call		X		
Distance acuity each eye*	X		X	X
Ocular alignment	X		X	X
Titmus Fly	X		X	
Randot Preschool Test	X		X	
ATS questionnaire			X	X

* Using ATS single-surround HOTV acuity testing protocol on study certified vision tester.

** For patients whose amblyopic eye acuity has improved by ≥ 1 line at the 12-week visit, visits occur every 12 ± 1 weeks until no improvement of one or more lines.

Additional visits can be performed at the discretion of the investigator. A Follow-up Examination Form should be completed for every exam (not just the minimum required exams).

Extension Studies after Primary Outcome

Efficacy of Intermittent Occlusion Therapy Glasses for Amblyopia-Dense, Deprivation and Myopic Anisometropia

Amblyopia

Approved 02/08/16

Amended: 05/12/16; 06/27/16; 06/29/16; 07/26/16, 09/13/16, 09/19/16, 09/27/16, 12/15/16, 01/26/17, 03/02/17, 06/20/17, 11/1/17, 12/19/17, 08/27/18, 12/18/18

For patients who are randomized in the control patching group, after primary outcome at 12 weeks, if the patients desire to use IO-therapy glasses for treatment, they can use IO-therapy glasses for treatment as an extension study. This will not apply for those patients with deprivation amblyopia.

Stereoacuity

Differences between treatment groups in stereoacuity at the 12-week outcome will be assessed using a comparison of the distributions with the exact Wilcoxon rank sum test.

Primary Analysis for Safety

Sound Eye Acuity Data

The loss of 2 or more lines in sound eye visual acuity from baseline to the 12-week masked exam will be tabulated for each treatment group.

Ocular Alignment

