If skin irritation occurs, the parent will be advised to put an emollient on the skin and discontinue use of the patch for a day. Patching could potentially decrease the visual acuity in the sound eye, although this is almost always reversible. However, this occurrence is extremely unlikely since the sound eye will have several hours without occlusion each day. The diagnosis and management of reverse amblyopia is left to the investigator's judgment. Patching could precipitate the development of an ocular deviation (strabismus), although this has been found to be very rare in previous studies and indistinguishable from the natural history of strabismus. If treatment precipitates the development of an ocular deviation (e.g., esotropia in child with hyperopia), the parent will be advised to have the patient see the investigator as soon as possible.

Risks of IO-therapy glasses

The children adjust to the flickering of the lens of the strong eye easily. At the beginning, IO-therapy glasses may induce a transient headache or some discomfort.

However, just like traditional patching, IO-therapy glasses could potentially decrease the visual acuity in the sound eye, although this is almost always reversible. However, this occurrence is extremely unlikely since the sound eye will have several hours without occlusion each day and the risk is the same with either the IO-therapy glasses or traditional patching. The diagnosis and management of reverse amblyopia is left to the investigator's judgment. So far, there is no significant decrease (≥ 2 lines logMAR) in the visual acuity in the sound eye reported.⁴

As with traditional patching treatment, IO-therapy glasses could precipitate the development of an ocular deviation (strabismus), although this has been found to be very rare in previous studies and indistinguishable from the natural history of strabismus. If treatment precipitates the development of an ocular deviation (e.g., esotropia in child with hyperopia), the parent will be advised to have the patient see the investigator as soon as possible.

Risks of microsensor

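### No systematic question at the 4-week call, and no table by arm, is described for headache or discomfort, skin irritation or sensor pressure

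*Combined protocol and SAP*

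**What the plan says.** Section 14 of the combined protocol and SAP names the tolerability effects. For the glasses: "At the beginning, IO-therapy glasses may induce a transient headache or some discomfort". For the patch: "If skin irritation occurs, the parent will be advised to put an emollient on the skin", together with advice to pause the patch for a day. Under the microsensor heading it adds that a badly fixed sensor can press on the skin. For both treatments it names reduced acuity in the sound eye and a new ocular deviation.

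Under Follow-up Interactions in section 11, families are telephoned "via telephone 4 weeks following the beginning of treatment to answer any questions and to encourage compliance with treatment". The next scheduled contact is the primary outcome visit at week 12 ± 1. In the schedule table the 4-week column is marked only for the call itself. An ATS questionnaire is marked at week 12 and later visits, with no description of its items, recall period or analysis. The same section also says "Additional visits can be performed at the discretion of the investigator", with a Follow-up Examination Form for every exam.

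Primary Analysis for Safety tabulates by arm a loss of 2 or more lines in the sound eye, new strabismus, and a change in deviation of 10 PD or more. It lists nothing else. Section 16 answers the question on risk protection with one line that assigns data safety monitoring to the IRB.

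**The concern.** The protocol itself describes the glasses symptom as early and transient, yet the first scheduled examination comes about 12 weeks after treatment starts. The one earlier contact is described in terms of questions and compliance. On noncompliance, the Notes in section 11 say that "the parents should be encouraged to persist with their efforts to treat to the best of their ability"; no step is described for recording whether a symptom was the reason.

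Tolerability is part of the case made for the device. Section 2 lists convenience, better compliance and "No allergy issues as with an eye-patch" among the benefits, and section 20 calls the study's risk minimal. The sample-size text says dropout is uncertain because the device is novel. If symptoms and reasons for stopping are not collected in the same way in both arms, the trial will have little to report on these points, and a difference in wear or dropout will be hard to explain.

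**Working it through.** **The plan's own figures.** No figure is given for tolerability, so there is none to correct. The denominator used below, 28 per arm, does reproduce from the Sample Size text (SD 0.14, difference 0.12, two-sided 5%, power 80%):

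- Normal approximation: n = 2 × [0.14 × (1.960 + 0.842) / 0.12]² = 21.4, so 22 per arm.
- Two-sample t-test: 22.4, so 23 per arm, as stated.
- Dropout of 15%: 23 / 0.85 = 27.1, so 28 per arm, as stated.

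**Each named effect against what is scheduled.**

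| Effect (section 14) | 4-week call | Week 12 ± 1 | Table by arm |
|---|---|---|---|
| Headache or discomfort, glasses | no question described | none described; questionnaire items not given | none |
| Skin irritation, patch | no question described | same | none |
| Sensor pressure on skin, glasses | no question described | same | none |
| Sound-eye acuity loss, both | not measurable by telephone | acuity measured | yes |
| New or larger deviation, both | no question described | alignment measured by SPCT | yes |

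Two of the five effects are tabulated and three are not.

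**Timing.** Week 12 ± 1 means 11 to 13 weeks from the start of treatment. A question at the 4-week call would cut the recall interval for a start-of-treatment symptom from about 12 weeks to about 4.

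**Who is covered.** Follow-up Interactions names the severe and deprivation groups: 56 + 15 = 71 of the 81 children. The 10 children with myopic anisometropic amblyopia are not named there, so it is unclear whether their families receive the call.

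**Expected counts.** The rates are assumptions, since the documents give none.

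- At 5%: 28 × 0.05 = 1.4 children per arm.
- At 20%: 28 × 0.20 = 5.6 children per arm.
- Chance of at least one case among 28: 1 − 0.95²⁸ = 76% at the low end and 1 − 0.80²⁸ = 99.8% at the high end.

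**What a count could support.** If all 28 children in an arm were asked and none had the symptom, the one-sided 95% upper bound would be 1 − 0.05^(1/28) = 10.1%. With 23 children it would be 1 − 0.05^(1/23) = 12.2%. Those bounds are meaningful only if every family was asked.

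**What it could not support.** Take assumed true rates of 30% and 10%, with 28 per arm. With full capture the 95% half-width is 1.96 × √[(0.3 × 0.7 + 0.1 × 0.9) / 28] = 20 percentage points. Power is for a two-sided 5% test of two proportions, normal approximation with pooled variance under the null:

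| Share of events recalled | Recorded rates | Difference | Power |
|---|---|---|---|
| 100% | 30% vs 10% | 20 points | 46% |
| 75% | 22.5% vs 7.5% | 15 points | 35% |
| 50% | 15% vs 5% | 10 points | 23% |
| 25% | 7.5% vs 2.5% | 5 points | 13% |

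Incomplete recall shrinks the recorded difference in proportion. Even with full capture the comparison is descriptive.

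**The case against.** The other side has several sound arguments.

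- *New strabismus is covered.* It is measured at enrollment and week 12 and tabulated by arm. This stands, and it limits the point on strabismus to onset and to deviations that resolve before week 12.
- *The forms are not shown.* The ATS questionnaire or the Follow-up Examination Form may contain tolerability items. This cannot be settled from the documents either way. Neither is scheduled at week 4, however, and no analysis of such items is stated.
- *Other channels exist.* Parents can raise symptoms on the call, extra visits are allowed, and the Notes require deviations from treatment to be discussed with the PI first. True, but spontaneous reports are unsystematic, and families who know their treatment may report differently by arm.
- *The trial is a small pilot, so any table would be imprecise.* Agreed. That argues for description rather than a test; it does not argue against asking.
- *The skin comparison is selective.* The severe cohort excludes children with known adhesive reactions, so a table would not test the background claim about skin problems in general. This stands and should be noted beside the table.
- *The effects differ in kind.* Only the glasses symptom is called early and transient; nothing says this of skin irritation. Sensor pressure is described as a fitting problem corrected by readjustment, and only the glasses are said to carry a sensor. Both remarks are fair.

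**Conclusion.** The point holds as a gap in collection and tabulation. For headache or discomfort, skin irritation and sensor pressure, the plan describes no systematic question at the only scheduled contact before week 12 ± 1, and no table by arm. Following the stated schedule would not reliably capture an effect that the protocol calls early and transient. The improvement is modest and inexpensive, and the efficacy comparison is untouched.

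A reader might go further and infer that tolerability cannot be compared at all, that staff do not ask why a child stops, or that such a child is recorded merely as noncompliant. The documents do not support these readings: the call script, questionnaire and form are not shown, and the text is silent on the last two. Nor do they show that these are the most frequent harms, because no rates are given. The 1 to 6 children per arm follow from assumed rates of 5% to 20% in 28 children. They are children whom no described procedure asks before week 12; calling them lost cases would also assume that nothing is captured at week 12.

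**What to change.** In section 11, Follow-up Interactions, add one short fixed list to the 4-week call, identical for both arms: headache or discomfort; skin irritation or pressure; a new eye turn noticed by the parent; days stopped and the reason. Repeat the list at week 12 on the Follow-up Examination Form. A reported eye turn follows the route that section 14 already sets. State whether the myopic anisometropic cohort also receives the call, and state the items and analysis of the ATS questionnaire.

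Under Primary Analysis for Safety, tabulate each item descriptively by arm and cohort with 95% confidence intervals. Label the data as unmasked parent report, and note the exclusion of children with known adhesive reactions from the severe cohort.

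The cost is a few extra minutes per call, one form section and one table. Because the answers can reveal the arm, someone other than the masked examiner should ask the week-12 questions, or they should follow acuity testing. No treatment rule, primary analysis or sample size changes.
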